**Table D7.3. Therapist Self-Report Measures**

CONSTRUCT	SCALE	NUMBER OF ITEMS
▪ Demographics	created for study	10
▪ Use of and comfort with technology	created for study	5
▪ Therapist experience with VillageWhere survey	created for study	6

*Note.* All therapist self-report items are administered only at the post-assessment time point.

**Exit interview.** After completing their self-report battery, therapists will participate in the same six-item open-ended exit interview used with parents and youth (see Appendix 16). The interview is expected to take 30-45 minutes to complete.

## **D8. Selecting Lottery Winners (among those enrolled and those never enrolled)**

Once all study procedures are complete for all participants, lottery winners will be selected. Recall that we seek to allocate lottery tickets to individuals in the recruitment pool (as an incentive to consider participation) as well as to those enrolled. A summary of how lottery tickets are to be allocated to each type of potential and actual participant appears in Table D8. Each parent-youth dyad can earn up to 6 chances to win, and each therapist, 4 chances.

Parents and Youth		Therapists	
Activity	# of Tickets Allocated	Activity	# of Tickets Allocated
Parent watches Family Recruitment Video	1	Watches Therapist recruitment video	1
Youth watches Family Recruitment Video	1	Watches Parent recruitment video	1
Parent agrees to be contacted by research team to learn more about study	1	Enrolls in study (whether a linked parent-youth dyad also enrolls or not)	2
Youth agrees to be contacted by research team to learn more about study	1		
Enrolled parent completes post-assessment within two weeks of end of usage period	1		
Enrolled youth completes post-assessment within two weeks of end of usage period	1		
Maximum possible lottery tickets:	6	Maximum possible lottery tickets:	4

A database of entries (excel spreadsheet) by participant /potential participant type (therapist or parent/youth) will be maintained in a password protected file on the MUSC homeroom drive. Ticket holder entries will appear on the spreadsheet in the order in which the entries were made (i.e., on the date and at the time the entry occurred, e.g., entry 37, therapist X watched video 1 on 6/16/14 at 2:05; entries 38 and 39, enrolled therapist Y could not participate because no one on caseload consented; etc.). An online random number generator will be used to select one number within the full set of entries obtained for each participant type (e.g., select a number between 1 and 39 for therapist entries, if #39 represents the last entry obtained in the therapist lottery). The individual or dyad who generated that entry will be the winner for that participant category. Winners will be notified immediately by email or phone, and arrangements will be made to ship the tablet computer directly from the retailer to the person's home or workplace. The value of each tablet computer (2 total) will not exceed \$300.

#### **D9. Participant Reimbursement.**

**Enrolled parents and youth.** All participating parents will receive \$25 for completion of the baseline assessment session and \$50 for completion of the post-usage session. Youth will receive \$10 for completion of the baseline assessment session and \$25 for completion of the post-usage session. Taken together, a parent-youth dyad that completes all study components will earn \$110. Compensation will be in the form of a check issued by other institution engaged in this research (the Evidence-Based Practice Institute), made out in the parent's name and mailed to the parent. Youth will not directly receive any compensation for participation.

When a parent elects to have a study phone provided for the youth, the youth will receive either 30 (in Field-Based Beta Testing) or 60 (in the Open Trial) days worth of phone usage (i.e., a prepaid phone card that includes voice, text, and data will be activated on the phone by study staff). The value of each month of service is approximately \$35.

Parents who either decide to keep a study phone or who fail to return it will have the actual cost of the phone deducted from the total family compensation earned. As noted above, phone costs are not yet known exactly but are not expected to exceed \$80. Thus, assuming a phone cost of \$80, a family who elects to keep the phone after the usage period is over and who completes all study procedures will receive \$30 (i.e., \$110-\$80). Parents will be given two weeks after the day they receive the self-addressed envelope to return the phone and will receive two reminders (by email or phone call) to return it. Any phone not received by the end of this two week period will be considered retained by the family. If a family receives a phone, fails to return it, and completes only a portion of study procedures that is insufficient to cover the cost of the phone, the parent will not be charged for the difference. For example, a parent and youth that complete the baseline but not the post-usage assessment will have earned only \$35, but will not be charged the balance of \$45.

Checks will be mailed to parents after all of the family's study procedures are complete and the phone's return status (if relevant) is known. A receipt outlining the components of the payment will accompany the check.

Note that in the parent-youth lottery drawing, the winner may or may not be someone who is enrolled in the study. If the winner is an enrolled participant, the tablet computer, valued approximately \$300, can be viewed as additional compensation.

***Enrolled therapists who do not participate.*** Some therapists will enroll, but not end up with a parent-youth dyad from their caseload also enrolled. Compensation for these participants will be two additional chances to win a tablet computer in the therapist lottery drawing. The lottery winner for the therapist drawing may or may not be someone who is enrolled in the study. If the winner is an enrolled participant, the tablet computer, valued approximately \$300, can be viewed as compensation. Also, all enrolled therapists can download the VillageWhere app to their personal smartphone if they so choose.

***Enrolled therapists who participate.*** Therapists will receive \$50 for participation, to be allocated in the form of a check immediately following their completion of the post-usage assessment session and exit interview.

## **D10. Data Management Procedures**

Participants will be assigned a participant identification number which will be used to label all data collected. A single list of participant names linked with ID numbers will exist in a password-protected electronic file stored on an MUSC homeroom drive accessible only to study staff. Research staff must use their personal identification numbers and passwords to access the homeroom drive itself.

Original signed copies of participant consent and HIPAA forms will be stored in a locked file cabinet in a locked office at the MUSC Family Services Research Center accessible only to the PI and the project manager. As a backup system in the event of fire or other physical damage to the building, scanned copies of these forms also will be created before filing and will

be uploaded to the MUSC secure homeroom drive created for this study. Participant ID numbers will not appear on consent and HIPAA forms.

The MUSC RedCap data collection system will be the primary means used for capturing self-report data. REDCap is a secure, web-based application for building and managing online surveys and databases. Participants will enter data directly into REDCap from their personal computers. REDCap provides automated export procedures for data downloads to Excel and common statistical packages (SPSS, SAS, Stata, R). In the event that any participant wishes to complete the questionnaires using hard copies, completed copies will be labeled only with participant ID numbers and will either be hand transported to MUSC by research staff or mailed to the Project Manager's MUSC research office by insured carrier (i.e., UPS or USPS). In no case will consent / HIPAA forms and questionnaires be transported or mailed together. Once paper versions of questionnaires arrive at MUSC they will immediately be scanned, uploaded as PDF documents to the MUSC homeroom drive, and entered into the RedCAP system. Once scanned copies and entered data are verified and checked for accuracy, original hard copies of questionnaires will be shredded.

App usage data and participant daily satisfaction ratings will be de-identified and stored on a server maintained by the Evidence-Based Practice Institute. The server used for data storage is the same one from which the app itself operates. The server is protected by a firewall, and is password protected. Only the PIs and research staff trained in procedures for conduct of ethical human subjects research will have access to data on the server. All data conveyed through the app will be secured by Secure Sockets Layer (SSL) encryption. SSL encryption is the same system used by banking and other commercial institutions and is considered to be the highest level or "gold standard" of online data protection. This technology is what is used for online purchases by encrypting the transmission of data between the web browser and the server that stores the data. Encryption keeps the data from being able to be viewed during transmission. Therefore, the data (which is already de-identified) cannot be viewed by others during transmission.

Individual exit interviews will not be recorded. Notes from these interviews will be labeled using only PIDs and participant type (parent, therapist, or youth).

## **D11. Data Analysis**

Data from demographics questionnaires and the Technology Use and Comfort Survey will be used to describe the sample itself. App usage and SUS data will be used to describe the success of the app itself. On the SUS, scores below a 3.5 on a five-point Likert scale (1 = poor; 2 = fair; 3 = good; 4 = very good; 5=excellent) will indicate a need for further app refinement in subsequent research. An aggregated mean score of 3.5 or higher will support app feasibility. App usage data will be aggregated and subjected to descriptive analyses to determine most preferred features and feature use sequences. Correlational analyses will link app usage data to participant satisfaction ratings and to measures of parent/youth behavior and functioning, to determine if certain app features were more highly preferred or more linked to changes in functioning than others.

Average scores on the SUS will also be compared between parents and adolescents. Between-group comparisons on the USAS will involve independent samples t-tests; effect size estimates also will be computed.

Pre- to post-usage change will be assessed on all parent and youth measures of functioning and behavior. Paired-samples T tests will be used and effect sizes obtained.

Qualitative data obtained from exit interviews will include annotations from investigators noting likes, dislikes, points of confusion, suggestions for improvement, misunderstandings, and potential unintended consequences. Qualitative data will be analyzed using a grounded theory approach (a data-reduction method for qualitative data used to generate and test hypotheses from the ground up).

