## **D4. Study Recruitment**

Since participation of the adolescent's therapist is required in order for a parent-youth dyad to be eligible for the study, therapists will be recruited first. Once enrolled, participating therapists will then assist in the recruitment of eligible parent-youth dyads from their existing caseloads. We seek a final sample size of no less than 24 therapist-parent-youth triads (i.e., 72 individual participants) who complete all study procedures. To account for potential premature participant dropout (e.g., youth is incarcerated in week 2; parent loses mobile phone service due to unpaid bills), we plan to enroll  $N = 30$  therapist-parent-youth triads. These triads will be allocated between the field test ( $n = 4-6$  triads) and the open trial ( $n = 20$ ).

Within each triad, all 3 participants must agree for any individual in the triad to complete study procedures. Among enrolled triads, all parent-youth dyads must be unique, but their linked therapist participants do not. If a given enrolled therapist's caseload yields more than one parent-youth dyad also enrolled, that therapist will be linked to more than one parent-youth dyad in the study. Thus, while the final sample size will be no less than  $n = 24$  parents and  $n = 24$  youth, it is possible that the number of enrolled therapists will be lower (e.g.,  $n = 12$  therapists, if each therapist had two parent-youth dyads from her caseload enrolled).

Conversely, we expect that for some enrolled therapists, we will be unsuccessful in recruiting any linked parent-youth dyads from their caseloads (due to disinterest in the study or ineligibility). To account for this possibility, we will continue to recruit and enroll therapists until an  $N$  of 24 parent-youth dyads completed is achieved. One implication of this approach is that more therapists may be enrolled in the study than will actually have the opportunity to engage in study procedures (e.g., we may need to enroll  $N = 40$  therapists to achieve  $N = 24$  parent-youth dyads).

The recruitment procedures that follow are informed by experiences recruiting therapists and having therapists refer parents and youth to the study during the formative evaluation of VW (previous protocol). As described below, two separate lottery drawings (one for therapists, one for parents/youth) will be used as one part of a more comprehensive recruitment strategy.

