Once both parent and youth baseline sessions are complete, the parent will receive a thank-you card by mail, thanking the family for completing the baseline assessment and informing them that \$35 compensation has been banked for them for the sessions (\$25 for parents, \$10 for youth; see below). The note will also remind parents that payment may take the form of a check made out to the parent or retention of the study-provided phone, and will be provided at the end of study procedures.

**Downloading the app.** Once both baseline sessions are complete, the parent and youth each will receive an email with a link to the VillageWhere server and his/her study-created password. The parent's activation email will be sent only to the parent; the youth's activation email will be sent to the youth and parent. Both activation emails will be sent immediately after both have completed the baseline assessment; participants will click on the link using their smartphone, enter their email address and password, and click to download the app. After this procedure is explained to the parent, the research assistant will offer to assist the parent or youth in downloading the app if desired, either immediately or in a subsequent phone call.

Research staff will monitor whether or not each participant has downloaded the app by looking on the server. If after one week of sending the initial activation email the participant has not downloaded the app, the research assistant will remind the participant to do so on day 7 (first reminder email) and every other day thereafter (days 9, 11, and 13) by email. If by day 14 the participant has still not downloaded the app, the research person will make two phone calls and two text message attempts to reach the participant during days 14-21. Participants who have not downloaded the app within 21 days of the baseline assessment session will be administratively withdrawn from the study.

The dyad's (parent and youth) app usage testing period will be considered to begin on the next calendar day after the second dyad member's app is downloaded (i.e., after whomever's app – parent's or youth's - is downloaded last).

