**Daily app satisfaction ratings.** During the evening of each day the app will prompt the participant with a pop-up notice to provide three brief Likert-scale ratings of their experience with the app that day. Daily rating questions for parents and youth appear in the App Use End of Day Ratings measure in Appendix 15. Parent ratings pertain to app helpfulness, satisfaction with the app, and sense of self-efficacy in managing youth behavior. Youth ratings pertain to feeling rewarded for good behavior, satisfaction with the app, and degree of hassle in using the app. When prompted the participant will click "OK" and be taken directly to a screen containing the three questions. When the participant has completed the questions the answers will be stored on the app server for later download at the end of the usage period. Participants can elect to not answer the questions when prompted, and prompts will not affect the participant's ability to use the phone.

**Qualitative exit interview.** Following their completion of the post-usage assessment battery, parent and youth participants will engage in a 30-45 minute open-ended interview, either in person or by phone, with a member of the research staff. (Most are expected to occur by phone). The interview provides an opportunity for participants to say in their own words their experiences using the app and suggestions for improvement. The interview consists of 2 questions for participants in the field-based beta test group or 6 questions for those in the open trial (see Appendix 16).

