## **E. PROTECTION OF HUMAN SUBJECTS**

### **E1. RISKS TO THE SUBJECTS**

#### *a. Human Subjects Involvement and Characteristics*

- Describe the proposed involvement of human subjects.

- Describe the characteristics of the subject population, including their anticipated number, age range and health status.

Three categories of human subjects will participate: 1) Parents of adolescents who are receiving mental health treatment, 2) adolescents receiving mental health treatment, and 3) therapists providing mental health treatment to parents and adolescents jointly. Participants will include at least 24 parents and 24 youth (at least 4 each in the field-based beta testing phase, 20 each in the Open Trial). Depending on problems encountered during the field test phase of the study, additional parents and youth might be needed to “debug” app problems prior to the open trial. The maximum number of parent and youth enrollees will not exceed 30 of each. Estimating therapist enrollment is difficult, because it is not yet known how many therapists will need to enroll in order to recruit a minimum of  $N = 24$  parent-youth dyads. We assume that a maximum  $N = 40$  enrolled therapists will be sufficient to recruit the parent-youth sample.

Parent and therapist age ranges will vary, but all will be adults (age 18 or older). Youth participants will range in age from 12-17 years old. All participants are expected to be physically healthy. In terms of mental health functioning, adolescent participants will be heterogenous, but all will have functional impairments sufficient to warrant their participation in either in-home or outpatient mental health treatment. Functional impairments may include internalizing symptoms (e.g., depressed mood, anxiety, social withdrawal), externalizing symptoms (e.g., oppositional behavior, drug or alcohol use), and failure to meet the developmental demands of their natural environments (e.g., to attend school, interact appropriately with peers, or refrain from criminal activity). A unifying factor across this heterogenous sample of adolescents is that all will be receiving family-oriented mental health treatment in which one goal is improved parental management of adolescent behavior.

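### The only numeric feasibility rule in D11 is scored on people who reach the post-usage session, and no uptake or completion rate over enrolled dyads is planned beside it

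*Combined protocol and SAP*

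**What the plan says.** **The rule.** D11 states: "An aggregated mean score of 3.5 or higher will support app feasibility". A lower score points to further refinement of the app. No denominator, missing-data rule or companion rate is attached. D11 also says that app usage data will help describe the app's success. The analyses it specifies for them are preferred features, feature sequences, and correlations with satisfaction and functioning.

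**When the SUS is given.** D1 and Tables D6.2a and D6.2b place it after usage only, for parents and youth. D6.2 confirms that a measure listed at one time point is given only then.

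**What happens to non-downloaders (D6.1, Downloading the app).** "Participants who have not downloaded the app within 21 days of the baseline assessment session will be administratively withdrawn from the study". The dyad's "app usage testing period will be considered to begin on the next calendar day after the second dyad" member has installed it. Download status is known: "Research staff will monitor whether or not each participant has downloaded the app by looking on the server".

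**Exit interviews (D6.2).** "Following their completion of the post-usage assessment battery, parent and youth participants will engage in a 30-45 minute open-ended interview".

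**Numbers.** D4: "We seek a final sample size of no less than 24 therapist-parent-youth triads", with 30 triads to be enrolled to allow for dropout, and therapist recruitment continuing until an N "of 24 parent-youth dyads completed is achieved". Section E1: "The maximum number of parent and youth enrollees will not exceed 30 of each".

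**Technology survey.** D11 uses it to describe the sample, but Tables D6.2a and D6.2b list its five items at post-test only.

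**The concern.** Aim 3 (Section A) is to find barriers to use and assess acceptability. D6.1 says the usage data should show whether, as well as how, real-world consumers are likely to use the app. A family that consents, completes baseline, is reminded by email, call and text, and still does not install is direct evidence on both questions. D11 has no place to count that family. A users' mean of 3.5 drawn from nearly all enrolled dyads means something different from the same mean drawn from far fewer, yet D11 words the conclusion identically. Section A makes the move to Phase II depend on promising Phase I results, so the wording matters.

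The technology survey has a related gap: it is missing for lost families, and those who do answer it have already been exposed to the app.

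**Working it through.** **Step 1. Trace an enrolled dyad with one non-downloader.**

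| Planned data source | Where | Available for this dyad? |
|---|---|---|
| SUS | D1, Tables D6.2a/b | No: the usage period never starts, so day 15 or 46 never arrives |
| App usage data | D6.1 | None from the member who did not install |
| Daily ratings | D6.2 | None from that member: the app issues the prompts |
| Parent and youth exit interviews | D6.2 | No: they follow the post-usage battery |
| Therapist survey and interview | D7.2, D7.3 | Not for this dyad; a therapist with another linked dyad is surveyed after the last one finishes |
| Download status | D6.1 | Yes, but D11 does not analyse it |

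**Step 2. Reproduce the plan's enrolment figure.** D4 states no dropout rate. The rate implied by 30 enrolled and 24 completing is 1 − 24/30 = 20%, and 24/(1 − 0.20) = 30. Because the 20% is back-calculated, this shows consistency only. Also 24 × 3 = 72 individuals, as D4 states.

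**Step 3. Loss the plan allows.** Completers are 20 open-trial dyads plus 4 to 6 field-test dyads, so 24 to 26. Enrolment is capped at 30.

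- 24 completers: loss 30 − 24 = 6, and 6/30 = 20%.
- 26 completers: loss 30 − 26 = 4, and 4/30 = 13%.

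**Step 4. What the added rates would look like.** Exact (Clopper-Pearson) 95% limits for x of n are the 2.5% quantile of Beta(x, n − x + 1) and the 97.5% quantile of Beta(x + 1, n − x). The counts are planned values used for illustration. The open-trial rows assume enrolment at the cap with all loss in that group: 30 − 4 = 26 or 30 − 6 = 24 enrolled. The field-test rows assume no loss.

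| Set | x/n | Rate | 95% CI | Width (points) |
|---|---|---|---|---|
| Whole study | 24/30 | 80% | 61% to 92% | 31 |
| Whole study | 26/30 | 87% | 69% to 96% | 27 |
| Open trial | 20/26 | 77% | 56% to 91% | 35 |
| Open trial | 20/24 | 83% | 63% to 95% | 33 |
| Field test | 4/4 | 100% | 40% to 100% | 60 |
| Field test | 6/6 | 100% | 54% to 100% | 46 |

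**Step 5. If the target is missed.** With 18 of 30 completing, the rate is 60% (41% to 77%); with 12 of 30 it is 40% (23% to 59%). If the completers' SUS mean is 3.5, D11 reads the same in each case as at 24 of 30.

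**The case against.** The strongest case on the other side is that this is a small, single-group Phase 1 study with a softly worded rule, that D11 names usage data beside the SUS, and that enrolment and completion are known anyway, so only a reporting line is missing. Much of that stands, and it rules out several stronger readings that a reader might infer:

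- **That the rule ignores unlimited loss.** If the targets are met, the cap of 30 and the floor of 24 bound loss at 6 dyads. Once the cap is reached, further loss also shows as fewer than 24 completers, so the completer count is not wholly silent.
- **That the 20% measures non-installation.** It is the allowance for all causes, and the documents give no figure for non-installation. D4's dropout examples are incarceration and lost phone service. Section E1 links extra dyads to debugging, so six planned losses is one reading of the 30. D4 also counts whole triads, so a triad can fail through its therapist or one dyad member while a SUS score exists.
- **That people who install and then stop using the app are excluded.** The post-usage session is booked at baseline and does not depend on use; if they attend, they are scored.
- **That the SUS mean is biased.** It is valid among users. It overstates feasibility for enrolled families only if loss relates to the app, and nothing in the documents shows that it will.
- **That reasons can never surface.** Reminder calls, or a therapist linked to several dyads, may reveal some. No analysis of such information is planned.

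None of this closes the gap. The named usage analyses describe features and sequences, and none gives a proportion of enrolled dyads.

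**Conclusion.** The point holds as a gap in what the feasibility conclusion can claim. D11's rule can declare feasibility without counting enrolled families who never installed, and no planned analysis shows whether their loss was related to the app. Under the plan's own targets, all-cause loss is 4 to 6 of 30 dyads (13% to 20%); this is an upper limit on missing SUS scores. If fewer than 24 complete, loss exceeds that and the verdict does not respond. This assumes that the cap of 30 is kept and that withdrawn participants are not given the SUS by some route the documents do not describe. It is an inexpensive improvement worth making, and it does not invalidate the SUS analysis.

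**What to change.** In D11:

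1. Label the SUS mean as a result among users who completed the post-usage session. Base the feasibility conclusion on it together with two rates over all enrolled dyads: both apps downloaded by day 21, and post-usage session completed by both members. Give exact 95% CIs for the whole study, counts by group (field test, open trial), and the recorded reason for each loss, so that losses unrelated to the app can be separated. No fixed minimum rate is needed. The planned 24/30 is a whole-study reference only: applied by group, 80% would fail an open trial that met the plan exactly (20/26 = 77%).
2. Give the five-item technology survey to parents and youth at baseline, so that it covers lost families and precedes app exposure.

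**Cost.** Download status is already monitored, and enrolment and completion are known. The additions are analysis wording, a reason-for-loss field if no form has one, and a small change to the assessment schedule submitted to the two IRBs. The feasibility statement may look less favourable, and the rates will be imprecise: CI widths are about 27 to 31 points for the whole study, 33 to 35 for the open trial and 46 to 60 for the field test, which is why counts are enough by group.
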